3.4 Measures

Unless otherwise noted all variables will be assessed at baseline and at follow-up, 3 and 6 months from baseline.

Primary alcohol outcome. We will use an **alcohol biomarker**: phosphatidylethanol (PEth) as the primary alcohol outcomes assessed at baseline and 6-month follow-up. PEth is a phospholipid which is formed only in the presence of alcohol and thus is highly specific.⁴⁷ PEth has shown good performance as a medium-term biomarker⁴⁸ and in controlled laboratory studies, correlated well with level of consumption (Spearman's $r = 0.6-0.8$).⁴⁹⁻⁵²

We will also use the AUDIT-C¹⁹ as another measure of hazardous alcohol use.

ART adherence: We will assess adherence to ART using the AIDS Clinical Trials Group Adherence measures (AACTG),⁵³ which includes recall questions about ARVs missed for the previous 4 days prior to the interview. It has demonstrated construct validity in Uganda and similar settings⁵⁴ and shows strong correlations with HIV VL⁵⁵ and moderate correlations with electronic adherence monitoring.⁵⁶

Measures and analysis for assessment of feasibility:

To inform a future larger randomized trial of the *KISOBOKA* intervention we follow Bowen et al.'s suggestions for conducting feasibility studies in preparation for larger RCTs²⁴ which includes assessing feasibility on the following dimensions: **acceptability, demand/use, implementation, and practicality**. We will document the number of intervention sessions participants attended which will speak to demand for/use of the intervention. To monitor implementation for the individual and group intervention sessions we will audio record intervention sessions and transcribe and code 20% of sessions to monitor intervention fidelity. Related to the practicality of the procedures, we will assess our retention rate through the 6-month follow-up to determine if we will need to develop additional retention procedures to maximize retention in a larger trial with a longer follow-up.

3.5 Data management and analysis

Data management

Pre-testing: We have used many of these measures in our prior research and already have English and Luganda versions finalized. The remaining measures will be pre-tested with staff

and patients at the participating clinics before the stage 1a pilot intervention. At this stage, we will also pretest the entire follow-up questionnaire to assess the duration of the interview and if necessary, remove measures to reduce the interview length. The stage 1ab pilot intervention will then be used for further pretesting and subsequent revisions to ensure the comprehensibility of each item before the stage 1b trial.

Field editing of data: Except for PEth and Viral load data all data will be entered into the CAPI (computer assisted personal interview) program as it is collected during the assessment interviews. A research assistant will double enter PEth viral load test results into the data file identified only by study ID number.

Qualitative data: Audio recordings of all qualitative data will be transferred to an encrypted and password protected computer. Electronic audio recordings of individual and group counselling sessions will be transcribed within 6 months of the session and the audio recordings will be destroyed once the information from the recordings is written down and double-checked for accuracy.

Quantitative data: Data for the baseline, 3 and 6-month follow-up questionnaires will be entered in real-time using KoboCollect software (A CAPI program). Using the KoboCollect system also eliminates the possibility of any out-of-range responses and therefore, data cleaning is not necessary. Data collected using Kobo is easily exported into SAS and other statistical programs for analysis. A research assistant will double enter PEth test results and viral load test results extracted from clinic records, into the data file identified only by study ID number. Clinical record data will be double entered by the research assistant into this same data file upon receipt. The double entered data will be checked and any discrepancies will be corrected by double checking the clinic records, and by comparisons with the laboratory report.

Data security: Data directly entered from the questionnaire interviews will be automatically encrypted and then uploaded onto a secure server. Only the PIs and data manager will have access to the server. No participant names will be stored in the database. All participants will be identified by a unique identifier, a random number assigned to them at the time of recruitment. In the event of loss of data or theft, all data files will be encrypted, and no outside user would be able to access the data. To ensure that no data that is collected is lost, encrypted data will be backed up on several sources: a separate server and copied to a secondary encrypted database used by the PI and biostatistician for additional processing.

Statistical Analysis Plan

A key objective of this study is to explore the effectiveness of the intervention vs. control and obtain effect size estimates to be used to design a future trial of this intervention. The primary outcomes are PEth scores, AUDIT-C score, and ARV adherence. Different statistical methods will be utilized depending on the type of outcome variable and whether minimum conditions for use of the methods are met. For example, log Gamma models may be used to analyze the difference in PEth scores between intervention and control groups given the expected distribution of PEth scores. An intent to treat approach will be utilized to determine analytic sample. Variables (except PEth which is measured at 2) will be measured at three time points (baseline, 3 and 6 months) so the dependency from the repeated measures must be considered. Information criterion such as AIC and BIC will be used to select the most appropriate covariance structure to address dependence. Generalized estimating equations (GEE) will be built to examine the intervention effect on our outcomes of interest across time points (baseline, 3 and 6 months), adjusting for repeated measurement, using a time*condition interaction term. Potential covariates for each adjusted model will be identified a priori from the literature and added to the model. Correlation matrices will be determined based on model fit. Statistically significant covariates will be retained in final fitted models using an alpha of 0.05.

4 Ethical considerations

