We will conduct a stage 1b pilot randomized controlled trial of the intervention. As a pilot study, this study is not powered to detect differences in outcomes, but rather to obtain reliable estimates of effect sizes for a subsequent efficacy trial. However, for illustrative purposes we explore power assuming a small effect size ($d= 0.2$) which is consistent with most brief MI-based alcohol intervention study effect sizes^{17, 25-27} as well as care engagement interventions.²⁸⁻³² **We plan to enroll 160 participants in the pilot intervention trial** with 80 in each arm i.e., randomizing to the KISOBOKA intervention arm (n=80) or to the control arm (n=80, alcohol screening and referral). To be conservative we anticipate 25% attrition. This will provide 72% power to detect an intervention effect and 85% power to detect a study arm x time effect.

Sampling procedure for the randomized pilot intervention trial (n=160).

The participants recruited (based on the inclusion and exclusion criteria) from the Mildmay HIV clinics in Wakiso District will be requested to share the research assistant's contact details (phone numbers) with their potentially eligible friends. This snowball-sampling procedure will enable us to reach more participants in this hard-to-reach population. Those interested in participating in the study will contact the research assistant who will then take them through subsequent eligibility screening and recruitment procedures. This process will be repeated until the required sample is attained.

Randomization for stage 1b randomized pilot intervention trial.

Individual-level randomization with permuted block assignment balancing 1:1 will be used to create equal size groups for the two study arms. Blocks of 8 or 10 study-generated ID numbers will be created and randomly assigned to intervention or control. Once a participant is screened as eligible and attends an enrollment/baseline visit they will be assigned a study-generated ID number from the pre-randomized list which determined their study arm assignment.

Study variables

Dependent variables

Primary outcomes:

- Phosphatidylethanol (PEth) (alcohol biomarker, blood sample)
- AUDIT-C score¹⁹
- ART adherence³³

Secondary outcomes:

- HIV care engagement
- HIV viral load obtained from clinic records
- Frequency of heavy/binge drinking

Potential covariates

- Receipt of instrumental and emotional social support³⁴

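### Does leaving the PEth model as an example, with no rule for undetectable values, make the pilot's PEth effect size unreliable?

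*Combined protocol and SAP*

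**What the plan says.** The Statistical Analysis Plan in section 3.5 lists PEth as one of three primary outcomes, with AUDIT-C and ART adherence. Its general rule on method is "Different statistical methods will be utilized depending on the type of outcome variable and whether minimum conditions for use of the methods are met". For PEth it adds that "log Gamma models may be used to analyze the difference in PEth scores between intervention and control groups", and gives the reason: "given the expected distribution of PEth scores". It then commits to GEE with an arm-by-time interaction, and on the analysis set it says "An intent to treat approach will be utilized to determine analytic sample".

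Section 3.4 explains that "PEth is a phospholipid which is formed only in the presence of alcohol and thus is highly specific", with measurement at baseline and 6 months. Section 3.3 names the laboratory method but gives no limit of detection. On software, section 3.5 says only that "Data collected using Kobo is easily exported into SAS and other statistical programs for analysis".

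The sample size part of section 3.2 describes the study as "not powered to detect differences in outcomes, but rather to obtain reliable estimates of effect sizes for a subsequent efficacy trial".

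**The concern.** Three things are left unwritten: what the minimum conditions are, which model replaces log Gamma if they fail, and how an undetectable PEth result is coded.

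They are linked. PEth forms only when alcohol is drunk, so a man who stops drinking may have a zero or undetectable value at 6 months, and the intervention is meant to make that more common in one arm. The Gamma likelihood requires a positive response, so zeros are an obvious way for its conditions to fail, and that would show only in the outcome data. GEE fixes the treatment of repeated measures but not the link, the scale or the effect measure. A log-link model for PEth and a linear model for log PEth would both fit the sentence on GEE.

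Because the pilot exists to supply effect sizes for a later trial, a planning estimate that depended on a late choice of scale could carry through to that trial's sample size.

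**Working it through.** The plan gives no PEth effect size to reproduce, so the check asks how far the missing rule can move the estimate under the model the plan names, and under others.

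**Inputs.** From the documents: 80 men per arm with 25% attrition, so 80 × 0.75 = 60 per arm; PEth at baseline and 6 months; log Gamma, GEE and intent to treat. Assumed, because the documents give no figures: mean PEth of 200 among drinkers in both arms, undetectable shares of 5% (control) and 15% (intervention), and an assay limit *L* between 1 and 20.

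**1. The analysis the plan points to.** Read in the usual way, a log Gamma model is a Gamma model with log link, so it estimates a ratio of means. With undetectable share *p* and substituted value *c*, an arm's mean is (1 − *p*) × 200 + *p* × *c*.

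| Coding | Intervention mean | Control mean | Ratio |
|---|---|---|---|
| Zero kept | 170 | 190 | 0.895 |
| *L*/2, *L* = 1 | 170.075 | 190.025 | 0.895 |
| *L*/2, *L* = 8 | 170.6 | 190.2 | 0.897 |
| *L*/2, *L* = 20 | 171.5 | 190.5 | 0.900 |

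The coding rule moves the ratio by at most 0.005. A second set of assumptions gives the same picture: median 200, log SD 1.2, limit 8, a ratio of 0.80 among detectable values, and 10% against 20% undetectable. Zeros kept gives 0.80 × 0.80/0.90 = 0.711; half the limit gives 0.713.

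**2. Whether the model can take zeros.** A log-link estimating equation with variance proportional to the squared mean accepts zeros. On a test set of 120 values with 12 zeros, such a fit and a quasi-Poisson fit both ran and gave the same ratio, 0.840. R's likelihood-based Gamma routine stopped with an error on the same data, so there the problem announces itself. Dropping the zeros would matter: in step 1 the ratio would become 200/200 = 1.00. But that would remove randomised men because of their outcome, against the intent-to-treat sentence.

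**3. Where large differences come from.** Take drinkers as log-normal with mean 200 and log SD 1, so their mean log PEth is ln 200 − 0.5 = 4.798. With *L*/2 substituted, the difference in mean log PEth is (0.15 − 0.05) × (ln(*L*/2) − 4.798).

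- *L* = 8: 0.10 × (1.386 − 4.798) = −0.341, and exp(−0.341) = 0.711.
- *L* = 1: 0.10 × (−0.693 − 4.798) = −0.549, and exp(−0.549) = 0.577.

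Over limits 1 to 20, and with exponential or log-normal drinkers, simulation gives 0.58 to 0.78, and 0.62 on log(PEth + 1). These are ratios of geometric means, a different quantity from the ratio of means. The documents mention neither a log transformation of PEth nor substitution. With equal undetectable shares of 15% and a 15% cut among drinkers, the ratios nearly agree (0.85 to 0.875). With no undetectable values and the same cut, all give 0.85.

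**4. Against sampling error.** For exponential drinkers the squared coefficient of variation in an arm is 2/(1 − *p*) − 1, which is 1.105 (control) and 1.353 (intervention). With 60 per arm, the standard error of the log ratio is √((1.105 + 1.353)/60) = 0.202. The 95% sampling range around 0.895 is therefore 0.60 to 1.33, about 2.2-fold. In pilots of this size the median spread between the log-link ratio and the two log-scale methods is 1.44-fold.

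**The case for a change.** The strongest reply is that the effect estimate is what this pilot is meant to deliver, so its being unpowered is no defence. The documents do not forbid a log-scale GEE. If the team changed scale after seeing zeros, the planning figure would change a good deal: in the 5% against 15% case, a standardised effect of 0.08 to 0.10 from the log-link model against 0.18 to 0.29 on the log scales, or 1,604 to 2,605 men per arm against 184 to 471 (80% power, two-sided 5%). Even with no undetectable values and a 15% cut, the figure runs from 598 to 1,033.

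Part of this stands. The text is loose, promises no check blind to arm, and leaves the scale formally open. But the sample-size contrast sets the plan's own example beside analyses it does not contain. Each figure is valid for a trial analysed on its own scale; it misleads only if an effect from one scale is carried into a trial analysed on another, and nothing in the documents suggests that. That the choice would be made after seeing the data by arm is an inference, since the plan does not say when conditions are checked. The wide gap in ratios also needs undetectable shares that differ between arms, and the documents give no shares.

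**Conclusion.** No change to the plan follows. The model for PEth is worded as an example, the conditions are undefined, and the assay limit and coding rule are absent; that is missing detail, not an error. The route indicated (log Gamma, GEE, intent to treat) has a natural reading: a log-link comparison of mean PEth that keeps every man with a sample, zeros included. On that reading the coding of undetectable values shifts the ratio by 0.005 or less in the case examined, far inside the pilot's own sampling range of 0.60 to 1.33.

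This rests on reading log Gamma as a log-link model for the mean, on zeros being kept as intent to treat implies, and on the assumed mean, shares and limits. It concerns one of three primary outcomes in a study that makes no confirmatory claim. An analyst would settle the rest from the laboratory report and state it with the results.

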3.3 Data collection

Stage 1b randomized pilot intervention trial (n=160):

Baseline data collection. After the informed consent process in a one-on-one interview (~60 minutes) using a computerized structured questionnaire, the interviewer will collect demographic information and detailed contact information (e.g., phone numbers, contact details of individuals who would know how to find the participant) to facilitate participant retention, and a venous blood sample for the alcohol biomarker measure (PEth).

Interviewers will set the appointments for the 3- and 6-month follow-up.

3 and 6-month follow-up data collection. For participants' convenience the 3-month follow-up interview may be conducted by phone whereas the 6-month follow-up interview must be in person since it involves obtaining a venous blood sample. For the 6-month follow-up, study interviewers will conduct follow-up data collection either at the study office at the clinic or, if requested by the participant, by meeting at a location of the participant's choosing. In our prior work in Uganda, we have found that participants who may have challenges in coming to the study office prefer to have the interviewer come to them. At 3- and 6-month follow-up the interviewers will conduct an individual structured interviewer-administered computer-based interview (~45 minutes duration). At the 6-month follow-up they will also collect 2mls of venous blood for PEth testing. If participants cannot be reached for the blood sample, we will still conduct the interview over the phone. This will allow us to still obtain some 6-month follow-up data from all participants. However, we will continue to follow up with these participants to obtain the venous blood sample even after the phone interview. Follow-up interviewers will be blinded to study arm assignment.

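### The PEth analysis names no method for missing data, although 25% attrition is expected and interview data that could inform the missing values will already be in hand

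*Combined protocol and SAP*

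**What the plan says.** Section 3.5, Statistical Analysis Plan: "Generalized estimating equations (GEE) will be built to examine the intervention effect on our outcomes of interest across time points", with a time-by-condition term and an intent-to-treat approach. Log-Gamma models are mentioned as a possibility for PEth. No missing-data assumption, weighting, imputation or sensitivity analysis is given. The three primary outcomes are PEth, AUDIT-C and ART adherence. PEth is measured only at baseline and 6 months; the other variables are also measured at 3 months.

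Section 3.2, sample size: "We plan to enroll 160 participants in the pilot intervention trial", 80 per arm, and "To be conservative we anticipate 25% attrition". The 25% is not split by arm, nor between men with no blood sample and men lost altogether.

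Section 3.3, follow-up: 6-month PEth needs blood drawn in person, but "If participants cannot be reached for the blood sample, we will still conduct the interview over the phone". Attempts to obtain the blood continue after that call, with no stated end date.

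**The concern.** A man with a 6-month phone interview and no blood has a 6-month AUDIT-C and no 6-month PEth. Because PEth has no 3-month value, he adds no follow-up to the PEth model. Ordinary GEE is not in general valid when dropout depends on outcomes that were observed but are not in the model. Here one such outcome, the 6-month AUDIT-C, is collected and measures the same behaviour.

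Selective loss is plausible: the background describes frequent mobility, and eligibility asks only that a man not plan to move within 6 weeks, against 6 months of follow-up.

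The pilot is meant to supply effect sizes for an efficacy trial, so bias in the estimate matters more than the significance test. Required sample size varies as 1/d². Reading a true 0.20 as 0.15 inflates the next trial by (0.20/0.15)² = 1.78; reading it as 0.25 shrinks it to (0.20/0.25)² = 0.64 of what is needed.

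**Working it through.** **From the plan.** 160 men, 80 per arm; 25% attrition; assumed effect d = 0.2.

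- Expected loss: 160 × 0.25 = 40 men, leaving 80 × 0.75 = 60 per arm if loss is equal.
- Standard error of a difference in standardised means at 60 per arm: √(2/60) = 0.183 SD.

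**The plan's own figure.** Section 3.2 states: "This will provide 72% power to detect an intervention effect and 85% power to detect a study arm x time effect". With d = 0.2 and 60 per arm, the noncentrality is 0.2/0.183 = 1.10. A two-sided 0.05 test (an assumption; the plan gives alpha only for covariate retention) then has about 19% power, so the 72% is not reproduced. That is a separate matter, and nothing below depends on it.

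**Assumed, because the plan does not give them.**

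- True effect −0.20 SD on both log-PEth and AUDIT-C.
- Correlations: baseline with 6-month PEth 0.5; 6-month AUDIT-C with 6-month PEth 0.6; baseline PEth with 6-month AUDIT-C 0.4.
- Missing PEth follows a logistic model in 6-month AUDIT-C, heavier drinkers being more often missing. The slope is per SD and the intercept is set to give the stated loss in each arm.

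**Three large-sample estimates of the 6-month arm-by-time effect.** (a) Available records under working independence. (b) Available records using baseline PEth, equivalent to a Gaussian GEE with the correct correlation. (c) As (b), also using 6-month AUDIT-C to predict missing PEth, with AUDIT-C known for every man.

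| Loss of 6-month PEth | (a) | (b) | (c) |
|---|---|---|---|
| 25% each arm, completely at random | −0.201 | −0.201 | −0.202 |
| 25% each arm, slope 1 in both | −0.201 | −0.201 | −0.201 |
| 25% each arm, slope 0.5 intervention, 1 control | −0.144 | −0.161 | −0.201 |
| 25% each arm, slope 1 intervention, 0.5 control | −0.258 | −0.240 | −0.201 |
| 30% intervention, 20% control, slope 1 in both | −0.250 | −0.235 | −0.201 |
| 20% intervention, 30% control, slope 1 in both | −0.152 | −0.167 | −0.200 |
| 20% intervention, 30% control, slopes 0.5 and 1 | −0.106 | −0.135 | −0.200 |
| 25% each arm, slope 1 in intervention only | −0.327 | −0.286 | −0.199 |

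**Reading the table.**

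- Rows 1 and 2: no bias.
- Rows 3 to 6, moderate differences between arms: the smallest bias is 0.200 − 0.167 = 0.033 and the largest 0.258 − 0.200 = 0.058. That is about 0.03 to 0.06 SD, or 15 to 30% of 0.20, in either direction.
- Rows 7 and 8, stronger differences: 0.065 to 0.127 SD.

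**Log-Gamma GEE.** Fitted to simulated log-normal PEth, this gave −0.14 to −0.28 in the settings of rows 3 to 6. These runs are noisy: the nominal Monte Carlo standard error is about 0.013, and settings with no expected bias returned −0.168 to −0.235. They show the same direction of shift and support no finer statement.

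**When some men have no 6-month interview.** Take slope 1 in the control arm, random loss in the intervention arm, and 25% missing in each. Available-case analysis gives −0.07 and the baseline-using estimate −0.11. Adding AUDIT-C gives −0.20 if every man without blood is interviewed, −0.16 if half are, and −0.14 if a quarter are. Recovery is then partial, but still closer to −0.20 than either alternative.

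**The case against.** **The method is inferred from silence.** The plan does not say that the GEE is unweighted or limited to available records. It keeps the choice of method open and refers to AIC and BIC for the covariance structure. This stands as far as it goes: nothing forbids weighting or imputation. But nothing provides for either, and a GEE fitted as described uses the records present.

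**Stronger readings that the documents do not support.**

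- A reader might infer that the planned GEE requires dropout to be completely at random. That is too strict. Loss may depend on modelled covariates, and equal loss with the same pattern in both arms leaves the contrast unbiased. A Gaussian GEE with the correct correlation also stayed at −0.20 when unequal loss depended only on baseline PEth, although that protection was not seen with the log-Gamma model (about −0.24).
- A reader might infer that the phone AUDIT-C data are wasted. They are not: AUDIT-C is a primary outcome. They are unused only as information about missing PEth.
- A reader might infer that the effect could be largely erased or reversed. Estimates such as −0.07 or +0.05 need selection in one arm only, or opposite selection in the two arms, and an estimator that ignores within-person correlation. The plan says that repeated measurement will be allowed for, and no passage indicates such dropout.
- A reader might infer that AUDIT-C repairs the problem completely. The −0.20 in column (c) is built in: missingness depends only on AUDIT-C, and AUDIT-C is known for everyone.
- A reader might take the difference in participation time (about 563 against 195 minutes) as evidence of differential loss. It is total time, paid at the same hourly rate in both arms, and says nothing direct about follow-up.

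**Mitigation and scale.** Section 3.3 offers collection at a place of the man's choosing and continued pursuit of the sample, which should reduce loss. The trial is a pilot, and the likely bias is smaller than its sampling error. Both points stand. They limit the size of the concern without removing the gain from using data already collected.

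**Conclusion.** The point holds as a moderate, cheaply corrected weakness in the PEth analysis. Where loss is related to drinking and differs moderately between arms (20% against 30%, or slopes of 0.5 against 1), the expected bias is about one sixth to one third of the standard error (0.03/0.18 to 0.06/0.18). It could run in either direction and grows only under more extreme arm-specific dropout.

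The correlations, the slopes and the arm-specific loss rates are all assumptions; the plan gives none of them. The benefit of the phone interviews also depends on how many men without blood are actually interviewed, which the plan cannot yet say.

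**What to change.** In section 3.5, specify for 6-month PEth an analysis that uses the interview data. One option is multiple imputation by arm, on a log or otherwise suitable scale, from baseline PEth, AUDIT-C at baseline, 3 and 6 months (phone interviews included) and adherence, followed by the planned GEE. An equivalent weighted GEE would also serve. Then:

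- report the available-case GEE alongside;
- add one delta-shift sensitivity analysis for men lost altogether;
- report missing PEth and missing interviews separately, by arm;
- record the date of each blood draw and examine late samples in a sensitivity analysis rather than discarding them.

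The cost is SAP wording and modest programming, with no new outcome data. The drawbacks are reliance on an imputation model fitted to about 60 observed PEth values per arm, and only partial correction for men with no 6-month interview.
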